#### 1.2.2 Randomization and Blinding

## Statistical Analysis Plan (SAP) – Phase 3 Segment

This study is double blinded. Approximately 6714 seronegative and 402 seropositive subjects 18 years of age and older will be randomized at a 2:1 ratio to receive either active investigational product (INO-4800, 2.0 mg) or placebo (SSC-0001). See [Table 1](#). Approximately half of seronegative subjects and approximately half of seropositive subjects will be 18-50 years of age, and the other half will be  $\geq 51$  years of age as is operationally feasible. Also, approximately 711 subjects will be  $\geq 65$  years of age, if operationally feasible.

Randomization in this trial will be conducted by YPrime. Subjects will be randomized in a stratified manner according to (a) age category (18-50 years vs.  $\geq 51$  years) on Day 0, and (b) presence of or absence on Day 0 of any of the following underlying medical conditions that increase risk of severe COVID-19 disease, per CDC criteria, as listed below:

- Cancer
- Chronic kidney disease
- Chronic lung diseases, including Chronic obstructive pulmonary disease (COPD), asthma (moderate-to-severe), interstitial lung disease, cystic fibrosis, pulmonary hypertension
- Neurologic conditions including stroke or cerebrovascular disease, that do not impact cognition
- Diabetes (type 1 or type 2)
- Hypertension
- Heart conditions, such as heart failure, coronary artery disease, or cardiomyopathies
- HIV infection (CD4 count  $>200$  cells/mm $^3$  or undetectable viral load)
- Liver disease
- Obesity (BMI  $\geq 30$  kg/m $^2$ )
- Sickle cell disease or thalassemia, or
- Smoking (current or former smoker).

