##### 3.1.3 Safety population (Safety)

The safety analysis population includes all subjects who receive at least one dose of study treatment. Subjects will be analyzed according to the treatments received.

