### 5.4 Safety Analysis

The safety endpoints include:

- The incidence of solicited and unsolicited injection site reactions.
- The incidence of solicited and unsolicited systemic adverse events (AEs) by system organ class (SOC), preferred term (PT), severity, and relationship to investigational product.
- The incidence of serious adverse events (SAEs).
- The incidence of adverse events of special interest (AESIs).
- The incidence of all-cause mortality.

Safety analyses will be conducted on the safety population and will be performed for all safety variables specified below. All safety data will be summarized and analyzed by treatment group and SARS-CoV-2 serostatus at baseline.

The safety analyses of changes from baseline to a specific time point in safety variables (e.g., laboratory parameters, vital signs, ECG) will only include subjects from the safety population who have data available from both the baseline and the time point under consideration unless otherwise specified.

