#### 5.4.1 Adverse Events and Deaths

All AEs will be classified by Primary System Organ Class (SOC) and Preferred Term (PT) according to the Medical Dictionary for Regulatory Activities (MedDRA) Version 23.0 or higher.

In summaries by SOC and PT, AEs will be sorted by descending frequency within each SOC and PT according to the total number of events. In summaries by PT, AEs will be sorted by descending frequency according to the total number of events.

AEs will be classified as pre-treatment or treatment emergent (TEAE) defined as follows:

- Pre-treatment: any AE that started before the first dose date of the study treatment
- TEAE: Any AE that was newly developed at or after the first dose date of study treatment.

Details for imputing missing or partial start dates of AEs are described in SAP section [3.5.2.1](#).

AE summaries will include the following:

- All TEAEs
- Related TEAEs (AE will be defined as related if causality is either probably, possible, or definite)
- TEAEs by maximum severity, including grade  $\geq 3$
- Medically Attended AEs
- TEAEs leading to treatment discontinuation
- Serious TEAEs
- TEAEs leading to death

All AEs, including injection-site reactions, will be summarized among the Safety Population by frequency per treatment arm. These frequencies will be presented overall and separately by dose, and will depict overall, by system organ class and by preferred term, the percentage of subjects affected. In addition, an overall summary for categories above will be prepared by treatment arm.

Where a subject has the same AE, based on preferred terminology, reported multiple times in the treatment period, the subject will only be counted once at the preferred terminology level in AE frequency.

Where a subject has multiple AEs within the same system organ class in the treatment period, the subject will only be counted once at the system organ class level in AE frequency.

Adverse events by severity and separately by relationship will be summarized based on the most intense event during the treatment period and strongest relationship to study treatment, respectively.

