The main summary of safety data will be based on events occurring within 30 days of any dose. For this summary, the frequency of preferred term events will be compared between study arms with risk differences and 95% confidence intervals, using the method of Miettinen and Nurminen. As this analysis will use many event categories, and produce many confidence intervals, caution should be exercised when interpreting these confidence intervals. Separate summaries will be based on events occurring within 7 days of any dose and regardless of when they occurred.

The following sample SAS code will be used to construct confidence intervals of the risk difference with the method of Miettinen and Nurminen:

```
proc freq data = <DATASET>;
  tables armcd * <OUTCOME> / riskdiff(CL=(MN));
run;
```

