## Statistical Analysis Plan (SAP) – Phase 3 Segment

- d. Intradermal injection(s) in skin preferably over deltoid region, or alternately over anterolateral quadriceps region, followed by EP at Day 0 and Day 28.
- e. Following administration of INO-4800 or placebo, EP data will be downloaded from the CELLECTRA® 2000 device and provided to Inovio.
- f. AEs to be collected from time of consent to Day 56; SAEs, MAAEs, and AESIs to be collected from time of consent to EOS.
- g. On Day 0, cellular sampling requires 64 mL of whole blood prior to 1st dose. At all other time points, collect 32 mL of whole blood. Cellular samples will be collected at selected clinical sites (estimated to include 711 subjects).
- h. On Day 0, humoral sampling requires a total of 17 mL of whole blood (two 10-mL red top serum collection tubes, each 8.5 mL of whole blood, to produce four serum aliquots of 2 mL each). At all other time points, collect 8.5 mL of whole blood in a single 10-mL red top serum collection tube to produce two serum aliquots of 2 mL each.
- i. SARS-CoV-2 antibody.
- j. The Day 0 RT-PCR results will not be required prior to dosing on that day.
- k. Day 42 visit must occur at least 10 days after Day 28 visit.
- l. Subjects will be evaluated during a "COVID-19 assessment visit" when acute COVID-19 is suspected. The assessment visit may be performed in the clinic, subject's vehicle, or at a home visit and should be completed within 3 days of symptom onset or within 3 days of a positive result of a SARS-CoV-2 test.
- m. For subjects with confirmed SARS-CoV-2 infection during the trial, a convalescent visit should be scheduled approximately 28 days after symptom onset, or in the absence of symptoms, the date of positive SARS-CoV-2 test. If acute symptoms are ongoing the site should follow up with the subject via phone call or unscheduled visit after symptom resolution or stabilization.
- n. Vital signs to be performed at COVID-19 assessment and convalescent visits include temperature, respiration rate, heart rate and oxygen saturation.
- o. Genotyping may also be performed on sample(s) collected at the COVID-19 assessment visit.
- p. Diaries to be used at selected sites only (estimated to include 711 subjects).
- q. Diary should be reviewed at the 14-day post-dose phone call or visit and collected at the next in-office visit.

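### Phase 3 solicited reactions are summarized over everyone dosed although diaries go to selected sites only, so absolute incidences and risk differences mix two kinds of ascertainment and are likely too low

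*SAP*

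**What the plan says.** All references are to the Phase 3 SAP unless stated otherwise.

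- **Endpoints (Section 5.4).** The first safety endpoint is "The incidence of solicited and unsolicited injection site reactions". The second covers systemic AEs, again both solicited and unsolicited.
- **Population (Sections 5.4 and 3.1.3).** "Safety analyses will be conducted on the safety population and will be performed for all safety variables specified below". That population is everyone dosed: "The safety analysis population includes all subjects who receive at least one dose of study treatment". It carries no condition about diaries.
- **Summaries (Section 5.4.1).** "All AEs, including injection-site reactions, will be summarized among the Safety Population by frequency per treatment arm", shown overall and by dose as the percentage of subjects affected.
- **Comparison (Section 5.4.1).** In the main safety summary, which covers 30 days after any dose, "the frequency of preferred term events will be compared between study arms with risk differences and 95% confidence intervals", by the Miettinen-Nurminen method. A shorter window follows: "Separate summaries will be based on events occurring within 7 days of any dose and regardless of when they occurred". No separate denominator is given for it.
- **Diaries (Appendix A, note p).** "Diaries to be used at selected sites only (estimated to include 711 subjects".
- **General AE collection (Appendix A, note f).** AEs are recorded from consent to Day 56, and SAEs, MAAEs and AESIs to end of study, with no restriction by site.
- **Planned size (Section 1.2.2).** "Approximately 6714 seronegative and 402 seropositive subjects 18 years of age and older will be randomized at a 2:1 ratio".

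**The concern.** A solicited reaction is one the subject is asked about. The only solicitation instrument this SAP names is the diary, and about nine in ten planned subjects would not receive one. Under Sections 5.4 and 5.4.1 those subjects still enter the denominator for solicited reactions, and they enter the numerator only if the reaction surfaces through general AE reporting. The resulting percentage is neither the incidence under solicitation nor the incidence under spontaneous reporting. It is a blend whose weights depend on how many sites happened to use diaries.

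The only rule restricting a safety analysis to subjects with data, in Section 5.4, concerns changes from baseline and does not reach reactions.

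The Phase 2 SAP has nearly the same sentence in its Section 7.7.1. There the schedule in Table 2 distributes diaries after each dose, with no selected-site limit in its notes, so the Safety population is a reasonable denominator. The Phase 3 text keeps that denominator although its schedule restricts diaries.

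At stake are the tolerability figures a reader would take from the trial. The revision history and Section 5.1.5 show that, after termination, analysis is confined to primary efficacy and safety and hypothesis tests are dropped. Safety estimates are thus a main remaining output. The error runs towards making the product look better tolerated.

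**Working it through.** **Inputs from the SAP.** Table 1 cells: 4476 and 268 on INO-4800, 2238 and 134 on placebo. Estimated diary subjects: 711 (Appendix A, note p). Allocation: 2:1.

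**Reproducing the planned total.** 4476 + 268 + 2238 + 134 = 7116, as stated. By arm: 4476 + 268 = 4744 on INO-4800 and 2238 + 134 = 2372 on placebo.

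**Diary share.** f = 711/7116 = 0.0999. Subjects without a diary: 7116 − 711 = 6405, a share of 0.9001.

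**Assumptions not in the SAP.** Let r be the incidence a diary would elicit, taken as equal at diary and non-diary sites. Let s be the share of those reactions that subjects without a diary still report as AEs, between 0 and 1 and equal in both arms.

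**Formula.** Safety-population rate = f·r + (1 − f)·s·r = r × (711 + 6405s)/7116. The attenuation factor is the inverse of the multiplier, 1/(0.0999 + 0.9001s). With equal s, the risk difference shrinks by the same factor; in the risk ratio the multiplier cancels.

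An illustration with assumed diary incidences of 40% on INO-4800 and 20% on placebo (true difference 20 points):

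| s | Multiplier | Attenuation factor | Reported rates | Reported difference |
|---|---|---|---|---|
| 0 | 0.100 | 10.01 | 4.0% vs 2.0% | 2.0 points |
| 0.25 | 0.325 | 3.08 | 13.0% vs 6.5% | 6.5 points |
| 0.5 | 0.550 | 1.82 | 22.0% vs 11.0% | 11.0 points |
| 1 | 1.000 | 1.00 | 40.0% vs 20.0% | 20.0 points |

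**Precision.** At 2:1 the diary subset is about 474 vs 237. The Wald half-width is 1.96 × √(0.4×0.6/474 + 0.2×0.8/237) = 6.7 points, so the interval is 20 ± 6.7. Over the whole population at s = 0 it is 1.96 × √(0.04×0.96/4744 + 0.02×0.98/2372) = 0.8 points, so 2 ± 0.8. The second interval is much narrower and excludes the value it is meant to estimate. This is the extreme case, shown to make clear that a larger denominator does not buy real precision here.

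**Dependence on enrolment.** At s = 0 the factor is the number dosed divided by the number with diaries. At planned size it is 7116/711 = 10.0. If, say, 4500 were dosed and the diary subset were full, it would be 4500/711 = 6.3. Section 2.2 says the trial ended before 75 cases. Neither actual number is given.

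**The case against.** The strongest reply is that AEs are collected from every subject to Day 56, and the Appendix A schedule carries the AE row through the visits and calls. Injection-site reactions at non-diary sites are therefore recordable. This stands. A reader might infer that subjects without a diary are simply counted as reaction-free, or that a tenfold dilution is to be expected. The documents support neither: tenfold is the limit when nothing is captured without a diary and enrolment is as planned. Likewise the multiplier equals the diary share only at s = 0.

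Second, the SAP does not say that the diary is the sole means of solicitation. Staff might ask about reactions at the Day 14 call, and such procedures normally belong to the protocol, which is not at hand. This also stands as a limit: the link from solicited to diary is an inference from the SAP naming nothing else. If active questioning took place everywhere, s would be higher and the attenuation smaller.

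Third, diary use follows site, not arm, and treatment is randomized, so ascertainment should affect both arms alike. A reader might infer a bias between arms; nothing in the documents shows one. Absolute rates and risk differences still shrink, and the risk difference is the measure the SAP chose.

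Fourth, one might conclude that the tables will fail to separate solicited from unsolicited events. The SAP text does not require separation, but table shells are in a separate document (Section 1), so the claim cannot be made about the tables themselves. The shells should not, however, have to override a population the SAP states explicitly.

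**Conclusion.** The point holds as a should-fix. The SAP fixes one denominator, everyone dosed, for events whose only named solicitation tool reaches an estimated 10.0% of planned subjects. Unless capture without a diary is complete, reported solicited incidences and risk differences will be too low. Even at half capture they fall to about 55% of the diary value.

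The size rests on planned enrolment, equal true incidence across sites, equal capture in both arms and the diary being the only solicitation tool. The capture share s and the numbers at termination are unknown, so no single factor between 1 and the upper bound of about 10 can be named as the expected one.

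Under equal capture, risk ratios are not distorted. SAEs, MAAEs, AESIs and deaths are collected irrespective of diaries and are not affected in this way, nor is the primary efficacy analysis. A reading that the whole Phase 3 safety evaluation is compromised therefore goes beyond the documents.

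**What to change.** In Section 5.4.1, with a matching entry in Section 3.1:

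1. Define a diary (reactogenicity) subset: Safety subjects who were issued a diary. An alternative is those with at least one diary entry after the relevant dose. State which. The first avoids conditioning on compliance after dosing; the second avoids counting blank diaries as no reaction.
2. Use this subset as both numerator and denominator for solicited local and systemic summaries and their Miettinen-Nurminen risk differences, overall and by dose.
3. Report unsolicited AEs separately on the full Safety population.
4. Report the actual number in the diary subset by arm beside the Safety population.

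The cost is one analysis flag, a few sentences of SAP text and any consequent change to the table shells. No new data are needed. Intervals for solicited events become wider, which reflects the information actually collected.

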### 5.4.2 Vital signs

Measurements for vital signs (pulse, blood pressure, SpO2, temperature, respiratory rate) as well as changes from baseline will be summarized with descriptive statistics. Visit values will be calculated as the mean of all available measurements per parameter.

## Statistical Analysis Plan (SAP) – Phase 3 Segment

---

### 5.4.3 Changes from Protocol-Specified Safety Analysis

Not applicable.

## 6. Appendices

### 6.1 Appendix A – Phase 3 Schedule of Events

Tests and assessments	Sc	D0	Tel #1	Wk 4	Wk 6	Tel #2-6	Wk 18	Tel #7-11	Wk 30	Tel #12-13	Wk 2	Tel #14-16	Wk 56	Illness	Illness		
	Screen a	Day 0		Phone call - Day 14 (±3d)	Day 28		Phone call - Days 56, 70, 84, 98, 112 (±5d)	Day 126 (±5d)		Phone calls - Days 140, 154-168, 182, 196 (±5d)	Day 210 (±5d)		Phone calls - Days 238, 266 (±5d)	Day 294 (±5d)		COVID-19 assessment visit b	COVID-19 convalescent visit c
		Pre	Post		Pre	Post		Day 42 (±5d) d	Day 126 (±5d)		Day 210 (±5d)	Day 294 (±5d)	Day 322-350, 378	Day 393 (±5d)			
Informed Consent	X																
Inclusion/Exclusion Criteria	X																
Medical history	X	X															
Demographics	X																
Socio-behavioral Assessment	X																
Concomitant Medications	X	X	X	X	X	X	X	X	X	X	X	X	X	X	X	X	
Physical Exam b	X	X		X	X	X	X	X	X	X	X	X	X	X	X	X	
Vital Signs	X	X		X	X	X	X	X	X	X	X	X	X	X n	X n	X n	
Height and Weight	X																
HIV Serology	X																
Pregnancy Test c	X	X		X													
INO-4800 or Placebo + EP d	X		X														
Download EP Data e			X		X												
Adverse Events f	X	X	X	X	X	X	X	X	X	X	X	X	X	X	X	X	
Cellular Samples g														X f	X f	X f	
Humoral Samples h														X f	X f	X f	
SARS-CoV-2 Serology i	X	X		X	X	X	X	X	X	X	X	X	X	X	X	X	
SARS-CoV-2 RT-PCR (Nasopharyngeal swabs)		X												X o			
Distribute Diary j			X		X												
Review/Collect Diary j				X	X		X										

a. Screening assessment occurs from -30 days to -1 day of Day 0. Screening and Day 0 visits may be combined if eligibility is able to be confirmed prior to dosing. If so, all assessments for Screening and Day 0 must be performed at the combined visit.

b. Full physical examination only at Screening and Day 393 (or EOS). Targeted physical exam at other indicated visits.

c. In women of childbearing potential. Urine pregnancy test at all indicated visits.

## Statistical Analysis Plan (SAP) – Phase 3 Segment

- d. Intradermal injection(s) in skin preferably over deltoid region, or alternately over anterolateral quadriceps region, followed by EP at Day 0 and Day 28.
- e. Following administration of INO-4800 or placebo, EP data will be downloaded from the CELLECTRA® 2000 device and provided to Inovio.
- f. AEs to be collected from time of consent to Day 56; SAEs, MAAEs, and AESIs to be collected from time of consent to EOS.
- g. On Day 0, cellular sampling requires 64 mL of whole blood prior to 1st dose. At all other time points, collect 32 mL of whole blood. Cellular samples will be collected at selected clinical sites (estimated to include 711 subjects).
- h. On Day 0, humoral sampling requires a total of 17 mL of whole blood (two 10-mL red top serum collection tubes, each 8.5 mL of whole blood, to produce four serum aliquots of 2 mL each). At all other time points, collect 8.5 mL of whole blood in a single 10-mL red top serum collection tube to produce two serum aliquots of 2 mL each.
- i. SARS-CoV-2 antibody.
- j. The Day 0 RT-PCR results will not be required prior to dosing on that day.
- k. Day 42 visit must occur at least 10 days after Day 28 visit.
- l. Subjects will be evaluated during a "COVID-19 assessment visit" when acute COVID-19 is suspected. The assessment visit may be performed in the clinic, subject's vehicle, or at a home visit and should be completed within 3 days of symptom onset or within 3 days of a positive result of a SARS-CoV-2 test.
- m. For subjects with confirmed SARS-CoV-2 infection during the trial, a convalescent visit should be scheduled approximately 28 days after symptom onset, or in the absence of symptoms, the date of positive SARS-CoV-2 test. If acute symptoms are ongoing the site should follow up with the subject via phone call or unscheduled visit after symptom resolution or stabilization.
- n. Vital signs to be performed at COVID-19 assessment and convalescent visits include temperature, respiration rate, heart rate and oxygen saturation.
- o. Genotyping may also be performed on sample(s) collected at the COVID-19 assessment visit.
- p. Diaries to be used at selected sites only (estimated to include 711 subjects).
- q. Diary should be reviewed at the 14-day post-dose phone call or visit and collected at the next in-office visit.
- r. When possible, cellular and humoral immunology samples will be collected. Cellular samples will be collected at selected sites only.
